6.5.1 Rescue Medications and Supportive Care

Participants should receive appropriate supportive care measures as deemed necessary by the treating investigator. For participants receiving lenvatinib plus pembrolizumab, suggested supportive care measures for the management of AEs with potential immunologic etiology along with the dose modification guidelines are outlined in Section 6.6. Where appropriate, these guidelines include the use of oral or IV treatment with corticosteroids, as well as additional anti-inflammatory agents if symptoms do not improve with administration of corticosteroids. Note that several courses of steroid tapering may be necessary as symptoms may worsen when the steroid dose is decreased. For each disorder, attempts should be made to rule out other causes such as metastatic disease or bacterial or viral infection, which might require additional supportive care. The treatment guidelines are intended to be applied when the investigator determines the events to be related to pembrolizumab or lenvatinib. Refer to Section 6.6.2 for guidelines regarding dose modification and supportive care.

It may be necessary to perform conditional procedures such as bronchoscopy, endoscopy, or other procedures as part of evaluation of the event.

6.5.1.1 Supportive Care Guidelines for Capecitabine

Please refer to the product label or local standards of care for capecitabine supportive measures.

6.5.1.2 Supportive Care Guidelines for Oxaliplatin

Please refer to the product label or local standards of care for oxaliplatin supportive measures.

6.5.1.3 Supportive Care Guidelines for 5-FU

Please refer to the product label or local standards of care for 5-FU supportive measures.

6.5.2 **Drug Interactions**

There are no DDI-related concomitant medication prohibitions or restrictions.

Lenvatinib is not expected to clinically meaningfully alter exposure to CYP3A4/ Pgp substrates based on results from a lenvatinib DDI study with midazolam (a sensitive CYP3A and Pgp substrate).

Clinical studies also showed that coadministration of lenvatinib with either inducers or inhibitors of CYP3A4/Pgp are not of clinical concern.

No drug interaction is expected between lenvatinib and pembrolizumab because of their divergent metabolic pathways. Pembrolizumab is a mAb and is primarily catabolized like other proteins, while lenvatinib is metabolized by enzymatic (CYP3A and aldehyde oxidase) and nonenzymatic processes (lenvatinib IB).

6.5.3 Concomitant Surgery

In general, surgical resection in participants who have metastatic disease is not encouraged except in exceptional cases as the benefit of surgery is unknown in this setting. However, if it is determined that participants are eligible for potential curative surgical resection, in the event of strong tumor response, please contact the Sponsor for guidance. Participants who have curative surgery while on study will be defined as are participants who have had tumor resection and a postresection imaging restaging to include at minimum contrasted CT chest, abdomen, pelvis, plus imaging of any part of the body previously known to have tumor and must show no residual disease. MRI with IV contrast or PET CT may be allowed if appropriate for restaging imaging. Participants who have surgery should continue imaging as detailed in the SoA (Section 1.3) until PD, or they otherwise meet the discontinuation criteria (Section 7.1).

105

6.6 Dose Modification (Escalation/Titration/Other)

Adverse events will be graded using NCI CTCAE v5.0. Investigators will decide the probability of the event being related to one or more drugs as to whether dose modification of one or more drugs is required.

This is an open-label protocol with a novel combination of pembrolizumab, lenvatinib, and chemotherapy (CAPOX or mFOLFOX6). Because of the multiple agents included in this protocol, overlapping toxicities may occur and the determination of the contribution of agents to specific toxicities may be challenging. Dose modifications can be handled individually or in concert depending on determined relatedness. Refer to Section 6.6.2, Section 6.6.3 and Section 6.6.4 for guidance with regards to dose interruption, dose modification, and overlapping toxicities. Please contact the Sponsor for additional guidance if needed.

Participants who interrupt or discontinue one of the study medications (pembrolizumab, lenvatinib, or chemotherapy) due to toxicity may continue with the other drug(s) in the combination until the criteria for treatment discontinuation are met (eg, unacceptable toxicity, disease progression).

6.6.1 Initial Treatment or First Course

08ZFCS

The number of treatments is calculated starting with the first dose. Participants who stop the combination or pembrolizumab after receiving 18 doses may be eligible for retreatment if they progress after stopping study intervention provided, they meet the requirements detailed in Section 6.6.6. Participants may be retreated in Second Course (Retreatment) for up to an additional 9 cycles (approximately 1 year).

6.6.2 Immune-Related Events and Dose Modification (Withhold, Treat, Discontinue)

Dose Modification and Toxicity Management for Immune-related AEs Associated with Pembrolizumab

AEs associated with pembrolizumab exposure may represent an immune-related response. These irAEs may occur shortly after the first dose or several months after the last dose of pembrolizumab treatment and may affect more than one body system simultaneously. Therefore, early recognition and initiation of treatment is critical to reduce complications. Based on existing clinical study data, most irAEs were reversible and could be managed with interruptions of pembrolizumab, administration of corticosteroids and/or other supportive care. For suspected irAEs, ensure adequate evaluation to confirm etiology or exclude other causes. Additional procedures or tests such as bronchoscopy, endoscopy, skin biopsy may be included as part of the evaluation.

Dose Modification and Toxicity Management Guidelines for irAEs associated with pembrolizumab monotherapy, coformulations, or IO combinations are provided in Table 5.

Table 5 Dose Modification and Toxicity Management Guidelines for Immune-related Adverse Events Associated With Pembrolizumab Monotherapy, Coformulations, or IO Combinations

General instructions:

- 1. Severe and life-threatening irAEs should be treated with IV corticosteroids followed by oral steroids. Other immunosuppressive treatment should begin if the irAEs are not controlled by corticosteroids.
- 2. Pembrolizumab monotherapy, coformulations or IO combinations must be permanently discontinued if the irAE does not resolve or the corticosteroid dose is not ≤10 mg/day within 12 weeks of the last treatment.
- 3. The corticosteroid taper should begin when the irAE is \leq Grade 1 and continue at least 4 weeks.
- 4. If pembrolizumab monotherapy, coformulations or IO combinations have been withheld, treatment may resume after the irAE decreased to ≤ Grade 1 after corticosteroid taper.

irAEs	Toxicity Grade (CTCAE v5.0)	Action With Pembrolizumab Monotherapy, Coformulations or IO Combinations	Corticosteroid and/or Other Therapies	Monitoring and Follow-up
Pneumonitis	Grade 2 Recurrent Grade 2, Grade 3 or 4	Withhold Permanently discontinue	 Administer corticosteroids (initial dose of 1 to 2 mg/kg prednisone or equivalent) followed by taper Add prophylactic antibiotics for opportunistic infections 	 Monitor participants for signs and symptoms of pneumonitis Evaluate participants with suspected pneumonitis with radiographic imaging and initiate corticosteroid treatment
	Grade 2 or 3	Withhold	Administer corticosteroids (initial dose of 1 to 2 mg/kg prednisone or equivalent) followed by taper	 Monitor participants for signs and symptoms of enterocolitis (ie, diarrhea, abdominal pain, blood or mucus in stool with or without fever) and of bowel perforation (ie, peritoneal signs and ileus) Participants with ≥Grade 2 diarrhea suspecting
Diarrhea/Colitis	Recurrent Grade 3 or Grade 4	Permanently discontinue		 colitis should consider GI consultation and performing endoscopy to rule out colitis Participants with diarrhea/colitis should be advised to drink liberal quantities of clear fluids. If sufficient oral fluid intake is not feasible, fluid and electrolytes should be substituted via IV infusion

irAEs	Toxicity Grade (CTCAE v5.0)	Action With Pembrolizumab Monotherapy, Coformulations or IO Combinations	Corticosteroid and/or Other Therapies	Monitoring and Follow-up
AST or ALT Elevation or	Grade 2 ^a	Withhold	Administer corticosteroids (initial dose of 0.5 to 1 mg/kg prednisone or equivalent) followed by taper	Monitor with liver function tests (consider weekly or more frequently until liver enzyme value returned to baseline or is stable)
Increased Bilirubin	Grade 3 b or 4 c	Permanently discontinue	Administer corticosteroids (initial dose of 1 to 2 mg/kg prednisone or equivalent) followed by taper	
T1DM or Hyperglycemia	New onset T1DM or Grade 3 or 4 hyperglycemia associated with evidence of β-cell failure	Withhold ^d	 Initiate insulin replacement therapy for participants with T1DM Administer antihyperglycemic in participants with hyperglycemia 	Monitor participants for hyperglycemia or other signs and symptoms of diabetes
	Grade 2 Withhold • Administer corticosteroids and initiate hormonal replacements as clinically		Monitor for signs and symptoms of hypophysitis (including hypopituitarism and adrenal insufficiency)	
Hypophysitis	Grade 3 or 4	Withhold or permanently discontinue ^d	indicated	insurrelency)
	Grade 2	Continue	Treat with nonselective beta-blockers (eg, propranolol) or thionamides	Monitor for signs and symptoms of thyroid disorders
Hyperthyroidism	Grade 3 or 4	Withhold or permanently discontinue ^d	as appropriate	

irAEs	Toxicity Grade (CTCAE v5.0)	Action With Pembrolizumab Monotherapy, Coformulations or IO Combinations	Corticosteroid and/or Other Therapies	Monitoring and Follow-up	
Hypothyroidism	Grade 2, 3 or 4	Continue	Initiate thyroid replacement hormones (eg, levothyroxine or liothyronine) per standard of care	Monitor for signs and symptoms of thyroid disorders	
Nephritis: grading according	Grade 2	Withhold	Administer corticosteroids (prednisone 1 to 2 mg/kg or	Monitor changes of renal function	
to increased creatinine or acute kidney injury	Grade 3 or 4	Permanently discontinue	equivalent) followed by taper		
Neurological	Grade 2	Withhold	Based on severity of AE administer corticosteroids	Ensure adequate evaluation to confirm etiology and/or exclude other causes	
Toxicities	Grade 3 or 4 Permanently discontinue		udinimister controosteroids	and of excitate other causes	
Myocarditis	Asymptomatic cardiac enzyme elevation with clinical suspicion of myocarditis (which was previously myocarditis Grade 1 using CTCAE v4.0)	Withhold	Based on severity of AE administer corticosteroids	Ensure adequate evaluation to confirm etiology and/or exclude other causes	
	Grade 2, 3 or 4	Permanently discontinue			
Exfoliative	Suspected SJS, TEN, or DRESS	Withhold	Based on severity of AE administer corticosteroids	Ensure adequate evaluation to confirm etiology or exclude other causes	
Dermatologic Conditions	Confirmed SJS, TEN, or DRESS	Permanently discontinue			

irAEs	Toxicity Grade (CTCAE v5.0)	Action With Pembrolizumab Monotherapy, Coformulations or IO Combinations	Corticosteroid and/or Other Therapies	Monitoring and Follow-up
	Persistent Grade 2	Withhold	Based on severity of AE administer corticosteroids	Ensure adequate evaluation to confirm etiology or exclude other causes
All Other irAEs	Grade 3	Withhold or discontinue based on the event ^e		
	Recurrent Grade 3 or Grade 4	Permanently discontinue		

AE(s)=adverse event(s); ALT= alanine aminotransferase; AST=aspartate aminotransferase; CTCAE=Common Terminology Criteria for Adverse Events; DRESS=Drug Rash with Eosinophilia and Systemic Symptom; GI=gastrointestinal; IO=immuno-oncology; ir=immune related; IV=intravenous; SJS=Stevens-Johnson Syndrome; T1DM=type 1 diabetes mellitus; TEN=Toxic Epidermal Necrolysis; ULN=upper limit of normal.

Note: Non-irAE will be managed as appropriate, following clinical practice recommendations.

- AST/ALT: >3.0 to 5.0 x ULN if baseline normal; >3.0 to 5.0 x baseline, if baseline abnormal; bilirubin;>1.5 to 3.0 x ULN if baseline normal; >1.5 to 3.0 x baseline if baseline abnormal
- AST/ALT: >5.0 to 20.0 x ULN, if baseline normal; >5.0 to 20.0 x baseline, if baseline abnormal; bilirubin: >3.0 to 10.0 x ULN if baseline normal; >3.0 to 10.0 x baseline if baseline abnormal
- c AST/ALT: >20.0 x ULN, if baseline normal: >20.0 x baseline, if baseline abnormal: bilirubin: >10.0 x ULN if baseline normal; >10.0 x baseline if baseline abnormal
- d The decision to withhold or permanently discontinue pembrolizumab monotherapy, coformulations or IO combinations is at the discretion of the investigator or treating physician. If control achieved or ≤ Grade 2, pembrolizumab monotherapy, coformulations or IO combinations may be resumed.
- Events that require discontinuation include, but are not limited to: encephalitis and other clinically important irAEs (eg. vasculitis and sclerosing cholangitis).

Dose Modification and Toxicity Management of Infusion Reactions Related to Pembrolizumab

Pembrolizumab may cause severe or life-threatening infusion reactions including severe hypersensitivity or anaphylaxis. Signs and symptoms usually develop during or shortly after drug infusion and generally resolve completely within 24 hours of completion of infusion. Dose modification and toxicity management guidelines on pembrolizumab associated infusion reaction are provided in Table 6.

Table 6 Pembrolizumab Infusion Reaction Dose Modification and Treatment Guidelines

NCI CTCAE Grade	Treatment	Premedication at Subsequent Dosing
Grade 1	Increase monitoring of vital signs	None
Mild reaction; infusion	as medically indicated until the	
interruption not	participant is deemed medically	
indicated; intervention	stable in the opinion of the	
not indicated	investigator	
Grade 2	Stop Infusion	Participant may be premedicated 1.5 h (±30
Requires therapy or	Additional appropriate medical	minutes) prior to infusion of study
infusion interruption	therapy may include but is not	intervention with:
but responds promptly	limited to:	Diphenhydramine 50 mg PO (or equivalent
to symptomatic	IV fluids	dose of antihistamine).
treatment (eg,	Antihistamines	Acetaminophen 500-1000 mg PO (or
antihistamines,	NSAIDs	equivalent dose of analgesic).
NSAIDs, narcotics, IV	Acetaminophen	
fluids); prophylactic	Narcotics	
medications indicated	Increase monitoring of vital signs	
for ≤24 hrs	as medically indicated until the	
	participant is deemed medically	
	stable in the opinion of the	
	investigator.	
	If symptoms resolve within 1 hour	
	of stopping drug infusion, the	
	infusion may be restarted at 50% of	
	the original infusion rate (eg, from	
	100 mL/hr to 50 mL/hr). Otherwise	
	dosing will be held until symptoms	
	resolve and the participant should	
	be premedicated for the next	
	scheduled dose.	
	Participants who develop Grade 2	
	toxicity despite adequate	
	premedication should be	
	permanently discontinued from	
	further study drug intervention.	

08ZFCS

PROTOCOL/AMENDMENT NO.: 015-08

NCI CTCAE Grade	Treatment	Premedication at Subsequent Dosing
Grades 3 or 4	Stop Infusion.	No subsequent dosing
Grade 3:	Additional appropriate medical	
Prolonged (ie, not	therapy may include but is not	
rapidly responsive to	limited to:	
symptomatic	Epinephrine**	
medication and/or brief	IV fluids	
interruption of	Antihistamines	
infusion); recurrence of	NSAIDs	
symptoms following	Acetaminophen	
initial improvement;	Narcotics	
hospitalization	Oxygen	
indicated for other	Pressors	
clinical sequelae (eg,	Corticosteroids	
renal impairment,	Increase monitoring of vital signs	
pulmonary infiltrates)	as medically indicated until the	
Grade 4:	participant is deemed medically	
Life-threatening;	stable in the opinion of the	
pressor or ventilatory	investigator.	
support indicated	Hospitalization may be indicated.	
	**In cases of anaphylaxis,	
	epinephrine should be used	
	immediately.	
	Participant is permanently	
	discontinued from further study	
A	drug intervention.	1:1 1 1:1 1:1

Appropriate resuscitation equipment should be available at the bedside and a physician readily available during the period of drug administration.

For further information, please refer to the Common Terminology Criteria for Adverse Events v5.0 (CTCAE) at http://ctep.cancer.gov

[figure not shown]
Other Allowed Dose Interruptions for Pembrolizumab

Pembrolizumab may be interrupted for situations other than treatment-related AEs such as medical/surgical events or logistical reasons not related to study therapy. Participants should be placed back on study therapy within 6 weeks of the scheduled interruption, unless otherwise discussed with the Sponsor. The reason for interruption should be documented in the participant's study record.

[figure not shown]
6.6.3 Lenvatinib Dose Modification and Toxicity Management

[figure not shown]
Lenvatinib dose modification during Safety Run-in (Part 1), induction, dose guidance to start consolidation, and dose modification during consolidation are specified below. Variation in dose modification guidance is because of differences in treatment regimen and recommended starting dose. Please refer to the section that applies to the correct phase of therapy (ie, induction or consolidation).

6.6.3.3 Management of QT Prolongation

Lenvatinib should be withheld in the event of development of QT interval prolongation greater than 500 msec. Lenvatinib should be resumed at a reduced dose when QTc prolongation is resolved to <480 msec or baseline. Monitor potassium, calcium and magnesium and replenish as appropriate.

6.6.3.4 Management of Hypertension

Hypertension is a recognized side effect of treatment with drugs inhibiting VEGF signaling. Investigators should therefore ensure that participants enrolled to receive treatment with lenvatinib have BP of ≤150/90 mm Hg at the time of study entry and, if known to be hypertensive, have been on a stable dose of antihypertensive therapy for at least 1 week before C1D1. Early detection and effective management of hypertension are important to minimize the need for lenvatinib dose interruptions and reductions.

Regular assessment of BP should be as detailed in the SoA (Section 1.3). Hypertension will be graded using NCI CTCAE v5.0, based on BP measurements only (and not on the number of antihypertensive medications). Refer to Appendix 8 (Figure 8, Figure 9) for additional information on the management of hypertension during Induction and Consolidation.

If the participant's first BP measurement of the current assessment is elevated (ie, systolic BP \geq 140 mm Hg or diastolic BP \geq 90 mm Hg), the BP measurement should be repeated at least 5 minutes later. One BP assessment is defined as the mean value of 2 measurements at least 5 minutes apart. If the BP assessment (ie, the mean of the 2 BP measurements obtained at least 5 minutes apart) is elevated (systolic BP \geq 140 mm Hg or diastolic BP \geq 90 mm Hg), a confirmatory assessment should be obtained at least 30 minutes later by performing 2 measurements (at least 5 minutes apart) to yield a mean value.

Antihypertensive agents should be started as soon as elevated BP (systolic BP \geq 140 mm Hg or diastolic BP \geq 90 mm Hg) is confirmed on 2 assessments at least 30 minutes apart. The choice of antihypertensive treatment should be individualized to the participant's clinical circumstances and follow standard medical practice. For previously normotensive participants, appropriate antihypertensive therapy should be started when systolic BP \geq 140 mm Hg or diastolic BP \geq 90 mm Hg is first observed on 2 assessments at least 30 minutes apart. For those participants already on antihypertensive medication, treatment modification may be necessary if hypertension persists.

Lenvatinib should be withheld in any instance where a participant is at imminent risk to develop a hypertensive crisis or has uncontrolled hypertension with significant risk factors for severe complications (eg, BP \geq 160/100 mm Hg, significant risk factors for cardiac disease, intracerebral hemorrhage, or other significant comorbidities). Once the participant has been on the same antihypertensive medications for at least 48 hours and the BP is controlled, lenvatinib should be resumed as described below.

Participants who have had systolic BP \geq 160 mm Hg or diastolic BP \geq 100 mm Hg must have their BP monitored on Day 15 (or more frequently as clinically indicated) until systolic BP has been \leq 150 mm Hg and diastolic BP has been \leq 95 mm Hg for 2 consecutive treatment

MK-7902-015-08 FINAL PROTOCOL 10-JUN-2025

08ZFCS

cycles. If a repeat event of systolic BP \geq 160 mm Hg or diastolic BP \geq 100 mm Hg occurs, the participant must resume evaluation until systolic BP has been \leq 150 mm Hg and diastolic BP has been \leq 95 mm Hg for 2 consecutive treatment cycles.

The following guidelines should be followed for the management of systolic BP \geq 160 mm Hg or diastolic BP \geq 100 mm Hg confirmed on 2 BP assessments at least 30 minutes apart:

- 1. Continue study drug and institute antihypertensive therapy for participants not already receiving this.
- 2. For those participants already on antihypertensive medication, the dose of the current agent may be increased, if appropriate, or 1 or more agents of a different class of antihypertensive should be added. Study treatment can be continued without dose modification.
- 3. If systolic BP ≥160 mm Hg or diastolic BP ≥100 mm Hg persists despite maximal antihypertensive therapy, then lenvatinib administration should be interrupted and restarted at 1 dose level reduction only when systolic BP ≤150 mm Hg and diastolic BP ≤95 mm Hg and the participant has been on a stable dose of antihypertensive medication for at least 48 hours.
 - If systolic BP ≥160 mm Hg or diastolic BP ≥100 mm Hg recurs on the first dose reduction despite optimal management of hypertension with antihypertensive medications (either by dose increase or the addition of a different class of antihypertensive), then lenvatinib administration should be interrupted and restarted at an additional dose reduction only when systolic BP ≤150 mm Hg and diastolic BP ≤95 mm Hg and the participant has been on a stable dose of antihypertensive medication for at least 48 hours.
 - If systolic BP ≥160 mm Hg or diastolic BP ≥100 mm Hg recurs on the second dose reduction despite optimal management of hypertension with antihypertensive medications (either by dose increase or the addition of a different class of antihypertensive), then lenvatinib administration should be interrupted and restarted at a third dose reduction only when systolic BP ≤150 mm Hg and diastolic BP ≤95 mm Hg and the participant has been on a stable dose of antihypertensive medication for at least 48 hours.
 - Additional dose reduction should be discussed with the Sponsor.

The following guidelines should be followed for the management of Grade 4 hypertension (life-threatening consequences):

- 1. Institute appropriate medical management
- 2. Discontinue study intervention

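### Section 6.6.3.4 puts a participant with confirmed BP of at least 160/100 mm Hg and significant risk factors under both a withhold and a continue instruction for lenvatinib, and leaves the dose after a risk-based hold unclear

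*Combined protocol and SAP*

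**What the plan says.** Section 6.6.3.4 deals with this blood pressure range in two places.

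The withhold paragraph reads "Lenvatinib should be withheld in any instance where a participant is at imminent risk to develop a hypertensive crisis or has uncontrolled hypertension". The second case is qualified: the participant "has uncontrolled hypertension with significant risk factors for severe complications". The examples in parentheses are a BP of at least "160/100 mm Hg, significant risk factors for cardiac disease, intracerebral hemorrhage, or other significant comorbidities". On resumption, once the participant has been on the same antihypertensives "for at least 48 hours and the BP is controlled, lenvatinib should be resumed as described below".

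The numbered list comes after it: "The following guidelines should be followed for the management of systolic BP" of at least 160 or diastolic BP of at least 100 mm Hg, confirmed on two assessments at least 30 minutes apart. Step 1 is "Continue study drug and institute antihypertensive therapy for participants not already receiving this". Step 2 covers participants already on antihypertensives, whose treatment is to be intensified, and adds "Study treatment can be continued without dose modification". Step 3 is the first to interrupt lenvatinib: "If systolic BP ≥160 mm Hg or diastolic BP ≥100 mm Hg persists despite maximal antihypertensive therapy". Restart is then one dose level lower, once BP is at most 150 systolic and 95 diastolic and the antihypertensive dose has been stable for 48 hours. Recurrences lead to further reductions. Grade 4 hypertension has a separate rule.

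The section also refers sites to Figures 8 and 9 in Appendix 8 for additional information on the Induction and Consolidation Phases.

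**The concern.** The same threshold appears under an instruction to withhold and under an instruction to continue, and a site treating a high-risk participant cannot tell from the text which to follow. The withhold paragraph is not confined to cases where antihypertensive treatment has failed. The numbered list is not confined to participants without risk factors.

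The first thing at stake is participant safety. Section 2.1 reports hypertension as the most frequent Grade 3 or higher treatment-related event with lenvatinib plus pembrolizumab in gastric cancer (38%). The second is consistency of exposure in Arm 1. Section 6.6.3.4 itself aims to keep lenvatinib interruptions and reductions to a minimum, and Section 4.3.2 argues that maximizing the dose may matter for long-term outcome. If sites resolve the text differently, interruptions and restart doses will partly reflect the reading and not only the participant.

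**Working it through.** No sample size, power or alpha calculation is involved. The check sets the trigger, action and restart of the two instructions side by side.

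1. **Trigger.** The withhold paragraph needs either an imminent hypertensive crisis, or uncontrolled hypertension together with significant risk factors. The numbered list needs only the confirmed BP.

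2. **Overlap on the narrow reading.** Take a participant with confirmed BP of at least 160/100 mm Hg, not controlled, and significant cardiac risk factors. The withhold condition is met. The numbered-list condition is also met, because it looks at BP alone.

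3. **Overlap on the wide reading.** The threshold is itself one of the listed examples. A site could take each example as enough by itself, and would then apply the withhold instruction to everyone with uncontrolled hypertension at that pressure. The overlap would no longer depend on any other risk factor.

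4. **Action.** The first text says withhold. Step 1 of the second says continue. Step 2 permits continuation. Step 3 interrupts only after maximal antihypertensive treatment has failed. For the participant in item 2 who has not yet had maximal treatment, the two texts point in different directions.

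5. **Precedence.** None is stated in the visible text. The section does separate out one category, Grade 4 hypertension, so it could have done the same for high-risk participants, but it does not.

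6. **Restart.** Both texts require 48 hours on unchanged antihypertensives. The withhold paragraph gives no numeric BP and no dose level of its own; it relies on what follows. What follows describes a first restart only in step 3, one level lower, for an elevation that outlasted maximal treatment. A participant held early because of risk factors does not fit that description. Whether the reduction applies to that participant is not stated. By contrast, the QT rule in Section 6.6.3.3 says directly that lenvatinib resumes at a reduced dose.

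**The case against.** The best case for the plan is that the withhold paragraph is a high-risk override and the numbered list is the general algorithm. The instruction to withhold attaches to imminent crisis, or to uncontrolled hypertension with risk factors, and not to a BP of 160/100 mm Hg as such. A reader who stops at the words "Lenvatinib should be withheld in any instance where a participant is at imminent risk to develop a hypertensive crisis or has uncontrolled hypertension" might infer a flat contradiction for every participant at that pressure. The full sentence does not support that. What stands is that the override is nowhere stated to be one, and that the placement of the threshold among the examples invites the wider reading.

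Step 2 is also only permissive, so withholding a participant already on antihypertensives would not breach it. Because antihypertensives start at a confirmed 140/90 mm Hg, many who reach 160/100 would already be treated. This softens the conflict for them. It does not remove it for those under step 1, and step 3 still implies that failure of maximal treatment is the trigger for interruption.

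A reader might also infer two rival sets of restart conditions. The documents do not support that either: the 48-hour element is the same, and the withhold paragraph defers to the later rules. Only the dose level after a risk-based hold is open.

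On size, it is tempting to apply the 38% from Section 2.1 to half of the 880 randomized participants: 0.38 × 440 = 167. That figure does not fit. It is the Grade 3 or higher rate among 29 participants who started lenvatinib at 20 mg, whereas Arm 1 starts at 8 mg and escalates only those who tolerate it. The disputed situation also requires risk factors, and entry is restricted to BP of at most 150/90 mm Hg without recent clinically significant cardiovascular disease or reduced ejection fraction. Nor is a large effect on dose intensity shown: in the solid-tumor study cited in Section 4.3.2, fatigue (26%) and diarrhea (23%) were more common reasons for reducing or interrupting lenvatinib than hypertension (17%).

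Finally, Figures 8 and 9 are not shown in the public text, and the lenvatinib dose-modification tables are redacted. They may settle precedence or restart dose, and their absence here is not a fault of the plan.

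**Conclusion.** The visible text of Section 6.6.3.4 gives two instructions that both cover a participant with confirmed BP of at least 160/100 mm Hg and significant risk factors. It does not say which governs, and it leaves the dose level after a risk-based hold unclear. That much holds even on the narrow reading of the withhold paragraph.

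It is a defect of wording with a bearing on safety. It is not a contradiction for all participants at that pressure, and it is not a clash of restart conditions. The documents give no rate for the combination of this BP with risk factors, so no number affected can be stated.

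The conclusion rests on the text alone. If Figures 8 and 9 set the order of precedence, what remains is to bring the text into line with them. No view is taken on which clinical rule is right.

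**What to change.** Reconcile the withhold paragraph, the numbered guidelines and Figures 8 and 9. The result should state:

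- which instruction governs at 160/100 mm Hg and above, separately for participants with and without the listed risk factors;
- whether that BP is meant as a sufficient example by itself or only in combination with other factors;
- which restart provision, including dose level, applies after a risk-based hold and after a hold for failure of maximal treatment.

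The content of these rules is for the sponsor's clinical team. The cost is rewording one section and checking two figures, with no effect on sample size, alpha or the analysis. The reach is limited: enrollment is complete (Section 9.9) and Amendment 8 supports close-out. Section 8.11.3 sets no duration limit for lenvatinib, however, so the correction still matters for anyone who remains on it.
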